3.3.4 Subgroup Analyses

Subgroup analyses will be conducted for primary efficacy endpoint in the FAS. Subgroups defined by the following will be evaluated:

- Sex (Male, Female)
- Use of triglyceride lowering drugs (fibrates, omega 3) (yes/ no)

Missing data will be handled using the same MCMC multiple imputation method and based on log-transformed data as the primary analysis.

A subgroup analysis of change and percent change from baseline in LDL-C at primary analysis time point will be performed in the FAS. Subgroups defined by the following will be evaluated:

- Statins use (yes/no)
- High/moderate intensity statins use (yes/no)

Table 4: Statin Intensity Classification (Stone NJ., et al, 2014)

| Statin (Preferred Term) | Intensity | | |
|----------------------------|--------------|----------------|-----------|
| | High | Moderate | Low |
| Atorvastatin | ≥ 40 mg | 10 to <40 mg | <10 mg |
| Rosuvastatin | ≥ 20 mg | 5 to <20 mg | <5 mg |
| Simvastatin | 80 mg | 20 to <80 mg | <20 mg |
| Pravastatin | | ≥ 40 mg | <40 mg |
| Lovastatin | | ≥ 40 mg | < 40 mg |
| Fluvastatin | | 80 mg | <80 mg |
| Pitavastatin | | ≥ 2 mg | < 2 mg |

*Dose is total daily dose

3.4 Pharmacokinetic and Anti-Drug Antibody analysis

3.4.1 Pharmacokinetic Data Analysis

All PK data analysis will be conducted using the PK Population except the listing of PK concentrations which will be conducted on the Safety Set.

The concentrations of ISIS 703802 in plasma expressed as ISIS 703802-equivalent (as total full-length oligonucleotides, including fully conjugated, partially conjugated, and unconjugated ISIS 703802) will be summarized by nominal visit by treatment group with and without stratification by patient ADA status using descriptive statistics. In addition, plasma terminal elimination half-life of ISIS 703802 will be calculated using the post-treatment follow-up data if data permits.

Additionally, for patients in the PK subgroup only, PK parameters will be calculated using non-compartmental methods. The maximum plasma concentration (C_{max}) and time to reach C_{max} (T_{max}) values will be obtained directly from the plasma concentration-time data. The area under the plasma concentration-time curve (AUC) values after the first dose (AUC_{0-24h}) and steady-state dose (AUC_{0-24h} and AUC_{tau}) will be calculated using the linear trapezoidal rule. Other PK parameters may be calculated at the discretion of the Sponsor. Plasma PK parameters will be summarized using descriptive statistics with and without stratification by patient ADA status.

Exposure-response relationships between selected lipid and PK measures (e.g., plasma trough concentrations) may be explored in a separate population PK/PD analysis combined with other clinical studies.

3.4.2 Anti-Drug Antibody Data Analysis

All ADA data analysis will be conducted using the Safety Set.

The ADA of ISIS 703802 will be assessed before, during, and after treatment with Study Drug (ISIS 703802 or placebo). The ADA incidence will be summarized by nominal visit and at the patient level by treatment group, as the total number of and percent of evaluated patients with ADA negative, positive, and unknown status. Patient ADA status (positive, negative or unknown) for all evaluable patients, along with the study day associated with the first emergence of ADA positivity (i.e., onset of ADA), the last positive ADA status observed, and peak ADA titer will be listed by treatment group. Potential relationships of ADA with selected efficacy, safety, and PK measures may be evaluated.

3.5 Safety Analyses

All safety analyses will use the Safety Set unless otherwise specified. Unless noted otherwise, denominators for all tables will be number of patients in the SS. For visit based safety endpoints including laboratory assessments, vital signs, and ECG, the analyses will use nominal visit collected by CRF. Early termination visit will be treated as Week 25/Week 27 for summary table.

Most AE summary tables, lab shift and abnormality tables will be based on two sets of data: on-treatment and on-study. On-treatment period is from the first dose through one dosing interval post last dose. For cohort A (weekly dose), on-treatment period spans time from first dose to the last dose

+ 7 days; For cohort B&C (every 4-week dose), on-treatment period spans time from first dose to the last dose + 28 days. On-study period is from the first dose until the patient's last contact date within the study.

Safety endpoints include the following:

- Adverse events
- Clinical safety laboratory tests
- Vital signs
- ECG

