### **8.8.1 *Follow-up Visits for Early Termination from Treatment Period or from Post-Treatment Follow-up Period***

Any subject who discontinues early from the treatment period or from post-treatment follow-up period should be followed as per the platelet monitoring rules shown in, [Section 8.6.3](#) for the first 6 weeks after discontinuing Study Drug and then at 8 (weekly dosing cohort) or 10 (every 4 week dosing cohorts) and 13 weeks post end of treatment period (as per visit schedule).

If the subject declines or is unable to participate in the above, the early termination visit procedures should be performed at the time of withdrawal, at a minimum, and ideally within 2 weeks from the last dose of Study Drug.

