**Appendix A Schedule of Procedures – Weekly Dosing**

Study Week	Screening r		Treatment Period												Follow-up Period			
	Run-in #	Qual †	1	1	5	9	13	17	21	25	26			27/ET	4*	8*	13*	
Study Day	-5 to -1	-1 to 0	1	2 a	29	57	85	113	141	169	176	177 a	178 a	183	*Weeks from the end of treatment period q			
Visit and Testing Window +/- Days	0	0	0	0	2	2	2	3	3	3	3	0	0	3	3	3	3	
Informed Consent	X																	
Outpatient Visit	X	X	X	X	X	X	X	X	X	X	X	X	X	X	X	X	X	
Inclusion/Exclusion Criteria	X	X	X															
Medical History	X																	
Vital Signs	X		X		X	X	X	X	X	X	X			X	X	X	X	
Physical Examination b	X		X		X		X							X	X	X	X	
Waist circumference/ WHR			X				X							X				
Body Weight and Height c	X	X	X		X	X	X	X	X	X	X			X	X	X	X	
12- lead ECG (triplicate)	X		X		X		X		X					X	X	X	X	
Ultrasound p	X																	
MRI		X d, s					X							X				
24-Hour Urine for Creatinine Clearance and Protein		X																
Extended Urinalysis e	X		EVERY 14 DAYS (+/- 2 days) e, f					X	X	X				X	X	X	X	
Renal Biomarkers g	X		EVERY 14 DAYS (+/- 2 days) f, g					X	X	X				X	X h	X h	X h	
Serum Creatinine and Cys-C i, j, k	X		EVERY 14 DAYS (+/- 2 days) f, i					X	X	X				X	X	X	X	
Chemistry Panel j, k	X		EVERY 14 DAYS (+/- 2 days) f					X	X	X				X	X	X	X	
Hematology j, k	X		X	HEMATOLOGY PERFORMED EVERY 14 DAYS (+/- 2 days) f, k												X h	X h	X h
Coagulation	X		X				X							X			X	
Hepatitis B, C, HIV	X																	
Thyroid Panel	X																	

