- n Serum and plasma samples will be collected and stored for follow-up exploration of laboratory findings and/or AEs (e.g., measurement of cytokine and/or chemokine levels, measurement of additional markers of kidney function, measurement of antibodies, etc.) and will be retained until completion of the final study report.
- o Last dose of Study Drug will be administered at Week 26/Day 176 +/- 3 days.
- p Ultrasound to determine positive liver fat at screening will only be performed on patients who do not have documented history of hepatic steatosis as determined by imaging (CT scan, MRI or US). Ultrasound may be repeated at the discretion of the PI. Results of Ultrasound must be available and confirm eligibility prior to MRI being performed.
- q Treatment period is defined as the time from the first dose through one dosing interval post last dose.
- r If a subject was screened and failed to meet eligibility under a previous protocol, the subject may be screened under the current protocol.
- s If a subject was screened and had an MRI, but failed to meet eligibility under a previous protocol, the MRI during rescreening may not need to be repeated. The need to repeat an MRI for such subjects should be discussed with the Medical Monitor.

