- n Serum and plasma samples will be collected and stored for follow-up exploration of laboratory findings and/or AEs (e.g., measurement of cytokine and/or chemokine levels, measurement of additional markers of kidney function, measurement of antibodies, etc.) and will be retained until completion of the final study report.
- o Last dose of Study Drug will be administered at Week 21/Day 141 +/- 3 days.
- p Ultrasound to determine positive liver fat at screening will only be performed on patients who do not have a documented history of hepatic steatosis as determined by imaging (CT scan, MRI or US). Ultrasound may be repeated at the discretion of the PI. Results of Ultrasound must be available and confirm eligibility prior to MRI being performed.
- q Treatment period is defined as the time from the first dose through one dosing interval post last dose.
- r If a subject was screened and failed to meet eligibility under a previous protocol, the subject may be screened under the current protocol.
- s If a subject was screened and had an MRI, but failed to meet eligibility under a previous protocol, the MRI during rescreening may not need to be repeated. The need to repeat an MRI for such subjects should be discussed with the Medical Monitor.

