A confirmed laboratory value is based on consecutive lab values within 7 days (no matter central lab data or local lab data). If consecutive value is the same or worse, then the initial value is confirmed. If the consecutive value is better, then the initial value is confirmed using consecutive value category. In essence, when the consecutive value is better, the initial value is not confirmed. If there is no retest within 7 days then the initial value is presumed confirmed. If there are multiple results on the same day (no matter from the same lab vendor or different lab vendors), then the worst value will be utilized in the analysis.

The following lab results will be graded per Guidance for Industry: Toxicity Grading Scale for Healthy Adult and Adolescent Volunteers Enrolled in Preventive Vaccine Clinical Trials (Sept 2007). The incidence of shift from baseline to worst post-baseline value will be summarized for on-treatment and on-study periods. Post-baseline lab results are defined as any assessment taken after the first dose no matter central lab or local lab data. If a patient is missing a baseline value but has a post-baseline value, then the baseline assessment will be labeled as “unknown”. Likewise, if a patient has a baseline value but has no post-baseline values, then the worst value will be labeled as “unknown”.

- Hemoglobin: shift from baseline to minimum post-baseline value
- WBCs: shift from baseline to minimum post-baseline value
- Platelets: shift from baseline to minimum post-baseline value
- BUN: shift from baseline to maximum post baseline value
- Creatinine: shift from baseline to maximum post-baseline value
- eGFR: shift from baseline to minimum post-baseline value
- Proteinuria: shift from baseline to worst post-baseline value
- ALT: shift from baseline to maximum post-baseline value
- AST: shift from baseline to maximum post-baseline value
- Alkaline phosphatase: shift from baseline to maximum post-baseline value
- Total bilirubin: shift from baseline to maximum post-baseline value

eGFR by will be graded using the following criteria:

- ≥ 90 mL/min/1.73m²
- ≥ 60 mL/min/1.73m² to < 90 mL/min/1.73m²
- ≥ 30 mL/min/1.73m² to < 60 mL/min/1.73m²
- ≥ 15 mL/min/1.73m² to < 30 mL/min/1.73m²
- < 15 mL/min/1.73m²

Shift tables for eGFR, ALT, AST and total bilirubin will be provided using confirmed values as well.

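### The on-treatment cut-off in SAP 3.5 falls on the target day of the end-of-treatment visit with no tolerance, so a compliant Week 25/27 sample can be classed off-treatment in the lab shift and abnormality tables

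*SAP*

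**What the plan says.** SAP 3.5 defines the period in words: "On-treatment period is from the first dose through one dosing interval post last dose". It then gives the day counts, which read from the Cohort A figure onward: "7 days; For cohort B&C (every 4-week dose), on-treatment period spans time from first dose to the last dose + 28 days". No tolerance is attached. Protocol Appendix A (footnote q in both schedules) defines the treatment period by the same rule, so the two documents agree.

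The definition decides which results enter one of two parallel sets of tables: "Most AE summary tables, lab shift and abnormality tables will be based on two sets of data: on-treatment and on-study". SAP 3.5.2 repeats this for the shift tables: "The incidence of shift from baseline to worst post-baseline value will be summarized for on-treatment and on-study periods". It also asks for the hepatobiliary, platelet and renal abnormality tables in both periods.

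Protocol Appendix A lets the last dose move. For Cohort A: "Last dose of Study Drug will be administered at Week 26/Day 176 +/- 3 days". For Cohorts B and C: "Last dose of Study Drug will be administered at Week 21/Day 141 +/- 3 days". The end-of-treatment visits are Week 27/ET (Day 183) and Week 25/ET (Day 169). The schedule row headed "Visit and Testing Window +/- Days" gives each of them 3 days either way.

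**The concern.** The cut-off and the visit share the same nominal day, but the visit has a window and the cut-off has none. A visit one day late, or an on-time visit after a last dose given one day early, complies with the protocol and still falls outside the on-treatment period. Which side a sample lands on is then a matter of scheduling, not exposure. Protocol 2.3.4 reports a terminal half-life of 3 to 5 weeks, so a few days past the interval does not mean the patient is off drug.

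The consequence is sharpest in Cohorts B and C. After Week 13, Appendix A schedules chemistry, creatinine with cystatin-C, and extended urinalysis at Weeks 17, 21 and 25. Samples are taken before dosing, so the Week 21 draw precedes the sixth dose. If Week 25 is off-treatment, the patient has no scheduled on-treatment ALT, AST, creatinine, eGFR, UACR or UPCR after that dose. A worst-value shift or a liver or renal threshold crossing first seen at Week 25 would then be missing from the on-treatment tables.

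**Working it through.** **Step 1. Reproduce the plan's target days.**
- Cohort A: 26 weekly doses from Day 1, so the last dose is 1 + 25 × 7 = Day 176. The cut-off is 176 + 7 = Day 183, the Week 27 target.
- Cohorts B and C: 6 doses 28 days apart, so the last dose is 1 + 5 × 28 = Day 141. The cut-off is 141 + 28 = Day 169, the Week 25 target.

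Both agree with protocol Appendix A and SAP Appendix A.

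**Step 2. Condition for falling outside.** Let d be the last-dose offset and v the visit offset from their target days, each from −3 to +3. The sample is off-treatment when v − d > 0.

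**Step 3. Count the allowed date pairs (7 × 7 = 49).**

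| Last-dose offset d | −3 | −2 | −1 | 0 | +1 | +2 | +3 | Total |
|---|---|---|---|---|---|---|---|---|
| Visit days outside, of 7 | 6 | 5 | 4 | 3 | 2 | 1 | 0 | 21 |

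21/49 = 42.9%. With the last dose on target, the days outside are 184 to 186 (Cohort A) or 170 to 172 (Cohorts B and C): 3/7 = 42.9%.

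**Step 4. From date pairs to patients.** The documents give no distribution of actual dates, so each row is an assumption. When both dates have the same distribution and are independent, P(v > d) = (1 − P(v = d))/2. Expected completers are 21 per group (SAP 3.2.5), or 4 × 21 = 84.

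| Assumed timing | Calculation | Share outside | Of 84 |
|---|---|---|---|
| Every visit exactly one interval after last dose | none | 0% | 0 |
| Dose on target, 80% of visits on target, rest even | 0.20 × 3/6 | 10% | 8.4 |
| 80% of both dates on target, rest even | (1 − [0.64 + 6 × (0.20/6)²])/2 | 17.7% | 14.8 |
| Dose on target, 50% of visits on target, rest even | 0.50 × 3/6 | 25% | 21 |
| Both triangular (weights 1, 2, 3, 4, 3, 2, 1 of 16) | (1 − 44/256)/2 | 41.4% | 34.8 |
| Both uniform | (1 − 7/49)/2 | 42.9% | 36 |

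That is 0 to 9 patients per group of 21. The share would be higher if visits tend to run late.

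**Step 5. Test the candidate repairs.**
- A flat +3 days: pairs with v − d > 3 number 3 (d = −3), 2 (d = −2) and 1 (d = −1), so 6/49 = 12.2% remain outside.
- Counting the in-window Week 25/27 sample as on-treatment: 0/49 remain outside. The largest overrun admitted is 3 − (−3) = 6 days.

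**The case against.** The case against making much of this is substantial.

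- **The SAP follows the protocol.** Both use the same definition, so there is no inconsistency, and widening it departs slightly from the protocol's wording. This stands and is a cost of the fix.
- **The value stays in the report.** By-visit summaries use the nominal visit, the on-study versions of the same tables include the sample, and all laboratory results are listed. Neither document ranks on-treatment above on-study. This stands: the sample is reclassified, not lost.
- **43% of patients.** A reader might infer that this share loses its end-of-treatment sample. The documents do not support that; 21/49 counts permitted date pairs. Protocol 8.1 keeps doses on a fixed weekday where possible and asks sites to aim for 7 days between the previous dose and a clinic visit. In Cohort A that pulls the visit onto the cut-off.
- **All on-treatment safety tables.** A reader might infer that adverse event and platelet tables are hit equally. Under SAP 3.5.1, events enter by their own start or end dates, not by visit. Hematology is drawn every 14 days, so a platelet count is due between the sixth dose and Week 25. In Cohort A, chemistry is also scheduled at Week 25.
- **Unscheduled retests.** Confirmed ALT or AST above 3 × ULN triggers at least weekly retesting (protocol 8.5.1), and SAP Table 1 admits unscheduled results. This helps only where an abnormality has already been found.
- **Nominal visits in SAP Table 1.** Table 1 names nominal scheduled and unscheduled visits as the source for shift and abnormality tables, and Appendix A lists Week 25/27 under the treatment period. One could read this as keeping the sample. But Table 1 says which records feed the tables, not which period they belong to. Unscheduled records can be placed only by date, so the dated rule in 3.5 governs.
- **No bias shown.** The rule treats active and placebo alike within a cohort. That is correct; the fault is arbitrary classification, not a demonstrated directional error.

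**Conclusion.** The point holds as a limited defect worth correcting. Under the dated rule, a protocol-compliant Week 25/27 sample is off-treatment for 21 of 49 allowed date pairs. The patient share is unknown: 0% to about 43% under symmetric timing, or 0 to 36 of 84 expected completers, with Cohort A probably low in that range if the 7-day instruction is followed. The effect is confined to the on-treatment lab shift and abnormality tables. It matters most for liver and renal results in Cohorts B and C, where Week 25 is the only scheduled chemistry and urine sample after the sixth dose within the treatment period.

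A reader might go further and want early-termination samples treated the same way. Protocol 8.8.1 asks for that visit "ideally within 2 weeks from the last dose of Study Drug", so a Cohort A sample on days 8 to 14 is off-treatment while the same sample in Cohorts B and C is on-treatment. The asymmetry is real, but it follows from defining the period by dosing interval. Admitting such samples would double the weekly arm's post-dose window for discontinuers and make its length depend on attendance. That is a debatable trade-off, and the argument here does not settle it.

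**What to change.** Add one sentence to SAP 3.5: for the on-treatment lab shift and abnormality tables, a nominal Week 25 (Cohorts B and C) or Week 27 (Cohort A) end-of-treatment sample taken within its protocol visit window (Days 166 to 172 or 180 to 186) counts as on-treatment even if it falls after last dose + 28 or + 7 days. Limit this to patients whose last scheduled dose was given within its own window. Otherwise a patient who missed that dose could have a much later sample counted.

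Do not rely on a flat +3-day extension, which leaves 6 of 49 pairs outside. Leave the on-treatment definition for adverse events unchanged.

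The cost is one sentence and a small programming rule, best settled before the end-of-treatment unblinding. A few samples taken up to 6 days past the dosing interval will count as on-treatment. The SAP should note this as a small departure from the protocol's treatment-period definition.

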3.5.1 Adverse Events

All adverse events will be coded by the MedDRA dictionary version 20.1. Missing or partial dates will be imputed as outlined as below under conservative principles:

Missing or partial start dates:

If year, month and day are all missing then assign the date of first administration of Study Drug

- If month and day are missing and year is:
 - the same as the year of the first administration of Study Drug then assign the month-day of first Study Drug
 - earlier than the year of the first administration of Study Drug then assign December 31
 - after the year of the first administration of Study Drug then assign January 1
- If only day is missing and month-year is:
 - the same as the month-year of the first administration of Study Drug then assign the day of first Study Drug
 - earlier than the month-year of the first administration of Study Drug then assign the last day of the month
 - after the month-year of the first administration of Study Drug then assign the first day of the month

Imputation will be performed for the end date only if the day or month is missing (i.e., year is present) for a resolved AE as follows:

- If month and day are missing and year is:
 - the same as the year of the last dose of Study Drug then assign the month-day of the last dose of Study Drug
 - otherwise, assign December 31
- If only day is missing then assign the last day of the month

If the imputed start date is later than the imputed end date then set the imputed start date to the imputed end date.

AE summary tables will be based on two sets of data: on-treatment period and on-study period defined in section 3.5. Imputed AE start date and end date will be used to determine whether AE is on-treatment or on-study. On-treatment AE summary tables include all AEs with imputed start date or

imputed end date fall in on-treatment period. On-study AE summary tables include all AEs with imputed start date or imputed end date after first dose date.

Treatment-emergent adverse events (TEAEs) are defined as adverse events that occurred after the first administration of Study Drug. An AE with a completely missing start date will be assumed to be treatment emergent. If the onset date/time is the same as or after the date/time of the first administration of Study Drug, then the event is considered to be treatment emergent. Note that imputed dates will be used for defining TEAEs.

Unless otherwise specified, the frequency of patients with any incidence of AEs and the number of events will be summarized by system organ class (SOC) and MedDRA preferred term (PT) for:

- TEAE
- TEAEs potentially related to Study Drug. Related is defined as “Related”, “Possible”, or missing relationship to Study Drug
- TEAEs by SOC, PT and severity. At each level of patient summarization, a patient with multiple events is counted only once according to the worst reported severity. Adverse events with missing severity will be categorized as “Missing” for this summary.
- TEAEs potentially related to Study Drug by severity
- Most common TEAEs by PT. Most common TEAEs are defined as an incidence of 10% or more within any treatment groups at preferred term level.
- Treatment-emergent serious adverse events (SAEs)
- Treatment-emergent SAEs potentially related to Study Drug
- TEAEs leading to permanent treatment discontinuation
- TEAEs leading to death.

Summary tables will be sorted by decreasing frequency of SOC and then by decreasing frequency of PT within SOC in Pooled ISIS 703802 column. If frequency is same for different PTs, sort alphabetically. If SOC or PT is missing, show as “Not Coded” in table.

An overview of AEs will be provided for all TEAEs. Treatment-emergent AEs, treatment-emergent SAEs, TEAEs potentially related to Study Drug, TEAEs that lead to treatment discontinuation, treatment interruption, dose reduction, and death. Original CRF collected dates will be used for listings.

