3.2.7 Patient Characteristics

Disposition and Protocol Deviations

Patient disposition, including reasons for premature discontinuation of treatment or follow-up, number of patients in Randomized Patients, SS, FAS, PPS, PK Population, and PK subgroup will be summarized for all screened patients. Listing of patient disposition will also be provided for Randomized Patients.

Major protocol deviations will be summarized by deviation category for Randomized Patients. All protocol deviations (major and minor) will be listed for Randomized Patients. Reasons for excluding patients from Per-Protocol Set will be summarized.

Demography and Baseline Characteristics

Patient demographic characteristics, including age (in years), sex, race, ethnicity will be summarized by treatment group for the FAS.

Baseline characteristics will include: weight (in kg) and weight by sex, height (in cm), BMI and BMI by sex, WHR, history of hepatic steatosis and years since diagnosis, history of confirmed type 2 diabetes mellitus and years since diagnosis, triglycerides, ANGPTL3, TC, LDL-C, HDL-C, VLDL-C, Non-HDL-C, ApoB (ApoB-48, ApoB-100), ApoC-III, ApoA-I, FFA, Lp(a), HbA1c, HFF, VAT, SAT, biomarkers of inflammation (IL-6, TNF-a, IFN-g) and adipokines (as available), and will be summarized by treatment group for the FAS.

Previous medical history will be summarized by treatment group for the FAS.

Medication

All medications will be coded by World Health Organization Drug Dictionary (WHODrug, Version DEC2017). Missing or partial dates will be imputed as outlined below under conservative principles.

Missing or partial start dates:

- If year, month and day are all missing then assign the date of first administration of Study Drug
- If month and day are missing and year is:
 - earlier than the year of the first administration of Study Drug then assign December 31
 - otherwise, assign January 1
- If only day is missing and month-year is:

- earlier than the month-year of the first administration of Study Drug then assign the last day of the month
- otherwise, assign the first day of the month

Imputation will be performed for the end date only if the day or month is missing (i.e., year is present) for a stopped prior/concomitant medication as follows:

- If month and day are missing then assign December 31
- If only day is missing then assign the last day of the month

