3.5.1.2 Treatment Emergent Flu-Like Reactions (FLR)

Treatment Emergent Flu-Like Reactions (FLRs) will follow two definitions:

- **Definition 1:** TEAEs with either (i) influenza like illness or (ii) at least one of following PTs: pyrexia, feeling hot, or body temperature increased, plus at least two of the following PTs: chills, myalgia, and arthralgia, starting on the day of injection or the next day.
- **Definition 2:** TEAEs with following PTs or verbatim: influenza like illness, chills, myalgia, arthralgia, pyrexia, feeling hot, or body temperature increased, starting on the day of injection or the next day.

Note that imputed dates may be used for defining FLRs.

Treatment Emergent FLRs defined in Definition 1 will be summarized by category (i) or (ii). Treatment Emergent FLRs defined in Definition 2 will be summarized by SOC and PT. Both definitions will be presented for on-treatment.

Percentage of injections leading to FLRs (Definition 2) for overall and by preferred term will also be summarized using descriptive statistics. Percentage of injections leading to FLRs will be calculated for each patient as $(A/B)*100$, where A is the number of injections associated with FLRs, and B is the total number of injections.

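### A year-only AE end date is set to the last-dose date even when the AE is recorded as starting later, so an event that began in follow-up enters the on-treatment tables

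*SAP*

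**What the plan says.** SAP 3.5.1 sets out the chain of rules.

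- **When an end date is imputed:** "Imputation will be performed for the end date only if the day or month is missing (i.e., year is present) for a resolved AE".
- **Year-only end date, last-dose year:** if the year is "the same as the year of the last dose of Study Drug then assign the month-day of the last dose of Study Drug".
- **Year-only end date, any other year:** "otherwise, assign December 31".
- **Start date with only the day missing:** if the month and year are "after the month-year of the first administration of Study Drug then assign the first day of the month".
- **Conflict between start and end:** "If the imputed start date is later than the imputed end date then set the imputed start date to the imputed end date".
- **Assignment to period:** "Imputed AE start date and end date will be used to determine whether AE is on-treatment or on-study". A start or an end inside the on-treatment period is sufficient for the on-treatment tables.

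SAP 3.5 ends the on-treatment period 7 days after the last dose in Cohort A and 28 days after it in Cohorts B and C. SAP 3.5.1.2 defines flu-like reactions (FLRs) by onset on an injection day or the following day, and adds: "Note that imputed dates may be used for defining FLRs". For year-only medication end dates, SAP 3.2.7 has no last-dose branch: "If month and day are missing then assign December 31".

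**The concern.** The last-dose branch does not look at the start of the event. Protocol 9.4.2 collects adverse events to the end of follow-up, so an event can begin weeks after the last dose, resolve in the same calendar year, and have only the year of resolution recorded. The rule then gives it an end date before its own recorded start. The last-dose date always lies inside the on-treatment window, so the event is counted there although the data place its onset outside.

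The stake is the on-treatment adverse-event tables, which are meant to show what happened under exposure, and possibly the FLR tables. With about 24 patients per group, a single misplaced event shows in the percentages.

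**Working it through.** No sample size or power figure is involved. The check applies the rules to dates.

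**Windows.** The last dose is on Day 176 (Cohort A) or Day 141 (Cohorts B and C), from Protocol Appendix A. Adding one dosing interval gives 176 + 7 = Day 183 and 141 + 28 = Day 169. These match the Week 27 and Week 25 target days in SAP Appendix A, so the windows are read correctly. Follow-up week 13 has target days 274 and 260 there.

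**Example.** Assume a first dose on 7 January 2019 and a resolved event with start recorded as September 2019 and end as 2019.

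| Step | Cohort A | Cohorts B and C |
|---|---|---|
| Last dose | 1 Jul 2019 | 27 May 2019 |
| On-treatment until | 8 Jul 2019 | 24 Jun 2019 |
| Start imputed | 1 Sep 2019 | 1 Sep 2019 |
| End imputed | 1 Jul 2019 | 27 May 2019 |
| Start after the conflict rule | 1 Jul (62 days back) | 27 May (97 days back) |
| On-treatment? | Yes | Yes |
| Starts on last injection day? | Yes | Yes |

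**Largest shift at target days.** 274 − 176 = 98 days in Cohort A; 260 − 141 = 119 days in Cohorts B and C.

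**Complete start date (10 September 2019).** The conflict rule speaks of the imputed start date.
- If that covers complete dates too, the start moves back 71 or 106 days.
- If it does not, the start stays and the end (1 July or 27 May) precedes it. The event is still on-treatment through its end date, but not on an injection day.

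The on-treatment error therefore arises under both readings. The injection-day error is certain only for a partial start.

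**Different end year.** With a last dose on 11 November 2019, start 20 December 2019 and end 2020, the end becomes 31 December 2020 and the event is correctly left out of the on-treatment tables. Two events alike in timing relative to dosing can thus be classified differently because of the calendar year alone.

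**Flu-like reactions.** A start moved to the last injection day meets the FLR onset test. One false FLR adds one injection to that patient's percentage of injections leading to FLRs: 1/26 = 3.8% in Cohort A, or 1/6 = 16.7% in Cohorts B and C, with all doses given.

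**Injection-site reactions.** SAP 3.5.1.1 also requires that the event did not resolve on the injection day or the day after. With start and end both on the last injection day, that test fails, so no false event is created. If imputed end dates are used there, which the section does not say, the rule would instead drop a true reaction to the last injection. The same reaction with its resolution date wholly missing would be counted.

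**Size.** One patient in 24 is 1/24 = 4.2 percentage points. For the 10% threshold for most common events in SAP 3.5.1, 2/24 = 8.3% is below and 3/24 = 12.5% is above, so one patient can move a term across.

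**The case against.** The strongest reply is that this is an edge case. The event must be resolved, have a year-only end date in the last-dose year, and have a known start in follow-up. Adverse events are reviewed at follow-up weeks 4, 8 and 13 (Protocol Appendix A), and SAP 2.5.1 provides edit checks and query resolution before lock, so few such records should survive. The rule is the same in every arm, and SAP 3.5.1 describes its imputations as conservative. All of this stands as a limit on size. It does not rescue the rule: placing an unknown date on treatment is conservative, but overriding a recorded start month or date is not.

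The medication comparison is also partial. SAP 3.2.7 contains the same start-reset sentence, and only its end-date branch differs.

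A reader might infer four stronger things that the documents do not support.

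- **That the rule manufactures injection-site reactions.** The persistence test in SAP 3.5.1.1 prevents it.
- **That every affected event is moved to an injection day.** For complete start dates this depends on how the conflict rule is read.
- **That events are shifted out of an after-drug category.** On-study runs from first dose to last contact and contains on-treatment, so overall on-study totals do not change.
- **That most follow-up events are affected.** If last-dose and onset dates are spread evenly over the year, the share of follow-up onset days in the last-dose year is the mean of 1 − t/365. For t = 8 to 98 this is 1 − 53/365 = 85%; for t = 29 to 119 it is 1 − 74/365 = 80%. These shares matter only for events that already have a year-only end date. They are upper limits, because the rule turns on the end year, which may be the next one. For one patient the share ranges from 0% to 100%.

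**Conclusion.** The rule is wrong as written, in a narrow set of records. A year-only end date in the last-dose year is placed on the last dose even when the recorded start is later, and that alone puts a follow-up event in the on-treatment tables. The added shift of the start to the last injection day, and with it a possible false FLR, holds for starts with only the day missing; for complete starts it holds only under the wider reading. An FLR is affected only if the option to use imputed dates is taken up.

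Treatment-emergent status, overall on-study totals and listings (which keep the collected dates) are untouched, and efficacy is not involved. The 4.2 points assume a group of 24 and a patient with no other event in the same row. The number of qualifying records is unknown and probably small. The correction is worth making because the result contradicts collected data and the change is cheap.

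**What to change.** In SAP 3.5.1:

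1. Impute a year-only end date of a resolved event as December 31 of that year, or the last contact date if earlier, and never before the event's start.
2. Where start and end conflict, adjust the imputed end. Never move a start earlier than its recorded day or month allows.

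In the example, with last contact at the target day, the event then runs from 1 September to 7 October 2019 (Cohort A) or to 23 September 2019 (Cohorts B and C). It is on-study only and does not start on an injection day. An event that truly began on treatment stays on-treatment through its start date. A true injection-site reaction to the last injection is no longer at risk of being dropped, unless last contact falls on that day or the next.

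Once this is done, there is little need to change the start-or-end inclusion rule or to bar imputed dates from the FLR definitions. The cost is two sentences in the SAP and a small programming change. Imputed event intervals become longer, which should be kept in mind wherever imputed end dates are used.
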